1.2 Associate Investigator(s) & Study Personnel

Will this study involve Associate Investigator(s) or other study personnel?	 Yes	 No
If Yes, Complete and submit the additional study personnel checklist .		

1.3 Risk Level

1.3.1 Does this study involve Minimal Risk or Greater than Minimal Risk?

 Minimal Risk	 Greater than Minimal Risk
--------------------------------------------------	----------------------------------------------------

If Minimal Risk, Proceed to Section 2.

If Greater than Minimal Risk, will this study enroll US DoD service members and recruit in a group setting? Yes No

If Yes, identify an ombudsman who will observe group recruitment of US DoD service members. Name: _____

If No, Please complete Section 2.

Note: Research involving Greater than Minimal Risk requires a Research Monitor. Contact 711HPW/IR for additional submission requirements.

Section 2: Facility / Contractor

2.1 Please identify the following:

Sponsor:	TriService Nursing Research Program	Funding Source and Amount:	TriService Nursing Research Program, \$359,258.00
Contract#; CRADA#; or Cooperative Agreement#:			
Location(s) where activity will be conducted:		Wright-Patterson Air Force Base: 711 th HPW and 88 th MDG	
Note: For locations outside of the 711 th HPW, local Commanders must give their permission for research to be conducted on individuals under their command. Contact 711HPW/IR for additional submission requirements.			

DISTRIBUTION C: Distribution authorized to U.S. Government agencies and their contractors (administrative). Other requests for, or further releases of this document, shall be referred to

[name].

Improving Resiliency in U.S. Air Force Healthcare Personnel
AFRL IRB APPROVED 1 SEPTEMBER 2020

Section 3: Conflicts of Interest

Principal and Associate Investigators are responsible for disclosing any of the following that would reasonably appear to be affected by their participation in or by the outcome of the study:

- Financial Interest
 - Anything of monetary value, including but not limited to; salary or other payments for services (e.g. consulting fees or honoraria), equity interests (e.g. stock options or ownership interests).
- Intellectual Property
 - Patents, copyrights and royalties from such rights, trademarks, tradenames and trade secrets.
- Any real or perceived personal conflict
 - Membership on a board of directors or advisory committee, having a commercial interest in the products or devices that are utilized in the study.

Note: All staff must complete the Conflict of Interest (COI) checklist and file it with the PI. The PI must submit their copy of the checklist with the IR submission package.

3.1 Do any members of the study staff have a COI?	 Yes	 No
----------------------------------------------------------	------------------------------	----------------------------------------

If Yes, Please explain in detail.

Section 4: Background and Scientific Rationale

Although the Department of Defense (DoD) has made substantial efforts to increase service member resilience, there is limited published evidence that these efforts increase resilience.¹⁻³ The RAND Center for Military Health Policy Research reviewed factors related to service members' psychological resilience and interventions to enhance it. They also assessed current resilience programs and found "generally very little rigorous research [...] across the different resilience factors"¹ (p. xvi), especially at family, unit, and community levels.¹ Across programs they found a lack of consistency in definitions of resilience, outcomes, and evaluation measures; they also reported that inadequate buy-in and logistical support from military leadership were barriers to program implementation.¹ The Institute of Medicine recommended the DoD utilize evidence-based resilience programs in 2013.⁴ In response, the DoD "reject[ed] the recommendation to eliminate programming judged by leadership to be beneficial, although not necessarily evidence based"⁵ (p. 3). Subsequent literature reviews have identified a continued lack of resilience program evaluation and inadequate evidence for the efficacy of military resilience programs.^{2, 3}

The proposed study will be guided by the Defense Centers of Excellence (DCoE) Resilience Continuum (Figure 1).¹ In the DCoE Resilience Continuum, psychological resilience is conceptualized as a process associated with maintenance and recovery of psychological health. Resilience has been variously defined as "the process of coping with or overcoming exposure to adversity or stress"¹ (p. xiii) and as a process of [...] negotiating, adapting to, or managing significant sources of stress or trauma"⁶ (p. 152). Resilience consists of "assets and resources within the individual, their life and environment"⁷ (p. 159) that promote a "capacity for adaptation and 'bouncing back' in the face of adversity"⁷ (p. 152). Resilience increases an individual's ability to adapt his or her "body, mind, and spirit to current life circumstances"⁶ (p.76). Resilience is considered to be a

DISTRIBUTION C: Distribution authorized to U.S. Government agencies and their contractors (administrative).

Other requests for, or further releases of this document, shall be referred to

[name].

Improving Resiliency in U.S. Air Force Healthcare Personnel

AFRL IRB APPROVED 1 SEPTEMBER 2020

protective factor against psychological problems for military service members and their families that is “characterized by hardiness, personal control, and positive coping strategies”⁸ (p. 47). However, few Department of Defense resilience training programs aimed to increase service member resilience had been empirically evaluated for their effectiveness in increasing resiliency.^{1, 3, 5}

Under the DCoE Resilience Continuum, optimal, mission-ready performance is sustained by providing supportive measures to service members and their families while engaging the support of leaders.¹ Such efforts enhance the service member’s ability to maintain a positive outlook and sense of purpose in the face of challenges. As service members encounter “challenges and stressors”¹ (p. 6), they can shift into the state of ‘Reacting’, and possibly deteriorate to the states of becoming ‘Injured’ or ‘Ill’.¹ Individuals experience an increasing severity and worsening symptoms of distress as they progress through these states.¹ Most service members are able to maintain a state of optimal, mission-ready functioning if they are provided “prevention and early intervention through education and training”¹ (p. 6). This training also helps service members to recover more readily to optimal performance when they experience stressors, unless the service member experiences a state of becoming ‘Injured’ or ‘Ill’, in which case medical treatment may be needed to recover to optimal performance.¹

Stress Management and Resilience Training. The Stress Management and Resilience Training (SMART) program was developed by [name]. SMART focuses on improving the practices of gratitude, mindful presence, kindness, and developing a resilient mindset.⁹ The SMART program incorporates practices that focus on six individual factors that have been found to promote individual-level resilience: positive coping, positive affect, positive thinking, realism, behavioral control, and altruism.¹ In this proposed study, SMART will be provided via either a two-hour, video teleconference (VTC) training or by completion of a self-paced, on-line version completed over a period of four to eight weeks. VTC or on-line versions will be utilized in order to assure the participants and researchers remain socially distanced to prevent transmission of severe acute respiratory syndrome coronavirus 2 (SARS-CoV-2). If in-person training is feasible and safe at a future time during the planned study period (Appendix A), in-person training will be used to supplement or replace VTC training.

To date, ten studies, most with small sample sizes, have been published to report the effectiveness of SMART in increasing resilience and/or decreasing stress.¹⁰⁻¹⁹ Four of these studies were experimental, and six were quasi-experimental designs. A majority of the studies examined the SMART intervention with physicians or nurses; however, non-healthcare personnel were included in three studies. Five published studies incorporated a two-hour version of the in-person SMART training.^{10-13, 15} Of these studies, three showed a 7.7% to 10.6% increase in CD-RISC scores, with a large effect ($d = 0.82 – 1.16$), eight to twelve weeks after training was completed and a significant decrease in self-reported stress.¹⁰⁻¹² Four of the six studies which utilized alternate forms of the SMART program showed that participant resilience significantly increased by 6.3% to 13.2% between twelve and thirty-six weeks after the program was completed.^{14, 17-19}

The SMART program has shown evidence of short duration efficacy when delivered via an in-person setting, but has not been tested with military personnel. To date, the effectiveness of the on-line

DISTRIBUTION C: Distribution authorized to U.S. Government agencies and their contractors (administrative).

Other requests for, or further releases of this document, shall be referred to

[name].

Improving Resiliency in U.S. Air Force Healthcare Personnel

AFRL IRB APPROVED 1 SEPTEMBER 2020

training, as well as, its equivalency with the in-person training has not been evaluated. This proposed investigation is necessary to determine if the training is as relevant to and effective with AF service members using an appropriately powered, quasi-experimental design. If the SMART program has similar effectiveness to that reported in studies with civilians, it would have the potential to be the kind of evidence-based resilience intervention that has, thus far, been lacking for military service members.

Section 5: Study Objective(s) and Purpose

5.1 Purpose

The purpose of this proposed study is to examine the effectiveness of the Stress Management and Resilience Training in increasing resilience in U.S. Air Force (USAF) healthcare personnel.

5.2 Primary Objective

The specific aim of this proposed quasi-experimental study is to examine the effectiveness of SMART in increasing levels of resiliency in active component USAF healthcare personnel (any 4XXX Officer or Enlisted Air Force Specialty Code [AFSC] assigned to 88th Medical Group (MDG) or U.S. Air Force School of Aerospace Medicine (USAFSAM) at Wright Patterson Air Force Base (WPAFB), OH.

To accomplish this aim, the following research question will be asked: Does SMART increase levels of resiliency in active component U.S. Air Force healthcare personnel?

5.3 Secondary Objective(s)

N/A

Section 6: Study Design

6.1 Description of Study Design

A pre/post-training quasi-experimental study is proposed to examine the effectiveness of the Stress Management and Resilience Training in increasing the levels of resiliency in healthcare personnel serving in the U.S. Air Force.

Intervention Group Assignment. Simple randomization will be utilized for participant assignment into the intervention delivery type (i.e. VTC group sessions or on-line SMART program). However, participants will be allowed to switch to their desired delivery type. We will track those individuals who chose to switch their randomized assignment. This will enhance our recruitment process and permit a component of randomized trial within a quasi-experiment. If in-person training becomes feasible and safe during the planned study period, in-person training will be used to supplement or replace VTC. Based on our estimation of the sample size needed and potential attrition, we will seek to enroll at least 60 participants into both the VTC and on-line training groups. We will assess the participants' level of resilience at baseline (enrollment) and at 12 weeks post SMART training. A second post-test will be attempted for participants who completed the SMART training no later than the end of February 2021 to test for longer-term changes in resilience.

DISTRIBUTION C: Distribution authorized to U.S. Government agencies and their contractors (administrative).

Other requests for, or further releases of this document, shall be referred to

[name].

Improving Resiliency in U.S. Air Force Healthcare Personnel

AFRL IRB APPROVED 1 SEPTEMBER 2020

Variables and Measures. Baseline data will be collected from each participant prior to the delivery of the intervention. The baseline survey will include nine demographics questions to attain information for participant age, gender, marital status, race, ethnicity, previous deployment, military grade/rank, duty location, and military job duty (i.e. AFSC). Participants' names and preferred e-mail and phone contact information will be requested. This information is necessary to arrange a follow-up phone call for each participant approximately four weeks after completing the SMART training and to send follow-up surveys via the Research Electronic Data Capture System (REDCap™; see Intervention) at weeks 12 and 24 (if applicable) after participants complete SMART. The baseline and follow-up surveys will also include the Connor Davidson Resilience Scale (CD-RISC)²⁰⁻²¹, Perceived Stress Scale (PSS)²²⁻¹³, Generalized Anxiety Disorder Scale (GAD-7)²⁴, and five-item Quality of Life (QoL) measures.²⁵

Change in resilience scores on the CD-RISC will be the primary endpoint of the study; secondary endpoints include changes in PSS, GAD-7, and the five-item QoL measure. Although stress, anxiety, and QoL are not primary outcome variables in this study, a decrease in stress and anxiety and an increase in QoL have been reported in past studies by participants who completed SMART, in addition to changes in resilience. Including the PSS, GAD-7, and QoL measure will offer an additional opportunity, with minimum response burden, to compare participant outcomes from this study with outcomes reported in previous studies.

Connor Davidson Resilience Scale. The CD-RISC has been utilized to measure service member resilience in multiple studies.^{21, 26-30} The 25-item scale was developed from multiple studies of the characteristics of resilient individuals.⁶ Respondents can answer each item using a five point Likert scale ranging from not true at all (0) to true nearly all the time (4).⁶ A total CD-RISC score is calculated by summing the score of all 25 items for a total possible score of 100, with a higher score reflecting a greater level of resilience.⁶

During the scale's development, an intraclass correlation coefficient of 0.87 was reported for test-retest reliability.⁶ The convergent validity of the scale was demonstrated by a strong positive correlation to the Kobasa Hardiness measure ($r = .83, p <.0001$), a strong negative correlation with the perceived stress scale ($r = -.76, p <.001$), and a modest negative correlation with the Sheehan Stress Vulnerability scale ($r = -.32, p <.0001$).⁶ The psychometric properties of the CD-RISC were favorable in a large sample of AF personnel ($N = 57,692$),²¹ in which the reported CD-RISC mean score was 83.66 ($SD = 11$), and Cronbach's alpha was .91.²¹

Perceived Stress Scale. The PSS was developed to provide a global measure and measure for current levels of perceived stress.²² The PSS is a 14-item instrument, and respondents answer each item on a four point Likert scale ranging from never (0) to very often (4).²² An individual's score is calculated by reverse scoring seven items and then summing all item scores, resulting in a score range of 0-56.²²

The test-retest reliability of the PSS has been reported to be .55 and .85.²² Concurrent and predictive validity of the PSS has been reported. The PSS and Center for Epidemiological Studies

DISTRIBUTION C: Distribution authorized to U.S. Government agencies and their contractors (administrative). Other requests for, or further releases of this document, shall be referred to
[name].

Improving Resiliency in U.S. Air Force Healthcare Personnel
AFRL IRB APPROVED 1 SEPTEMBER 2020

Depression Scale were shown to concurrently and independently predict psychosomatic symptoms.²² The PSS has predictive validity for utilization of health services ($r = .20, p < .001$), social anxiety ($r = .37, p < .001$) and smoking cessation rates ($r = .39, p < .001$).²²

Generalized Anxiety Disorder Scale. The GAD-7 is a brief measure of anxiety. Respondents can answer each item using a four point Likert scale ranging from not at all (0) nearly every day (3).²⁴ A total score is calculated by summing the scores of the seven items with possible scores ranging from 0-21.²⁴ Scores between 5-9 are indicative of mild anxiety, and score between 15-21 are indicative of severe anxiety.²⁴

During the scale's development, an intraclass correlation coefficient of 0.83 for test-retest reliability was reported.²⁴ Construct validity for the GAD-7 scale was demonstrated by a significant ($p < .05$ for all comparisons) positive correlations to disability days ($r = .27$), physician visits ($r = .22$), and symptom related disability ($r = .63$).²⁴ The convergent validity of the scale was demonstrated by a statistically significant, positive correlations to the Beck Anxiety Inventory ($r = .72$) anxiety subscale of the Symptom Checklist ($r = .74$), and Patient Health Questionnaire for Depression ($r = .75$).²⁴ In a previous study, the SMART program demonstrated a decrease in participants' reported levels of general anxiety (*Estimated Treatment Effect = -1.74, 95% CI = -4.7, +1.22*).¹³

Linear Analogue Self-Assessment (LASA) Quality of Life. A five-item LASA QoL measure will be used for this study. The 5-item LASA QoL measure includes the overall QoL measure, as well as, measures of physical, emotional, spiritual, and intellectual QoL.²⁵ Participants will respond to each item using a 10-point Likert scale ranging from as bad as it can be (0) as good as it can be (10).³¹ Although each item is scored separately and represents a distinct aspect of quality of life, the reported Cronbach's α for all five items suggests they share a common underlying construct.²⁵

The LASA overall quality of life item has been utilized as a brief, minimal burden assessment of QoL in clinical practice and clinical trials.³¹ The LASA overall QoL mean score for an healthy individual has been reported as 8.3 ($SD = 10.2$), and a score ≤ 5 can indicate a clinical concern.³¹ A lower LASA overall QoL scores is correlated with a worse performance status, and an increased likelihood of reporting a clinically meaningful deficit.³¹ In a previous study, the SMART program demonstrated a positive effect on participants' QoL (*Treatment Effect = +1.2, 95% CI = 0.0, 2.4, p = .044, d = .83*).¹²

Intervention. SMART is focused on improving the practices of gratitude, mindful presence, kindness, and developing a resilient mindset.⁹ In this study, SMART will be offered via a two-hour VTC training provided by [name] or [name] or via a self-paced on-line course. The two-hour VTC will be provided synchronously to a maximum of 10 individuals. A study team member will contact participants in the VTC group to provide available dates and times of scheduled classes, and these participants will be scheduled for a class they would like to attend. Participants in the VTC group will be provided a web-link prior to the session, and each session will have a unique password to access the training. Participants in the on-line training group will be provided a code to access the training website. If local conditions permit in-person group meetings (i.e. Health Protection Condition

DISTRIBUTION C: Distribution authorized to U.S. Government agencies and their contractors (administrative).
Other requests for, or further releases of this document, shall be referred to
[name].

Improving Resiliency in U.S. Air Force Healthcare Personnel
AFRL IRB APPROVED 1 SEPTEMBER 2020

[HPCON] Alpha or Bravo), in-person group SMART training in a classroom will be offered as an alternative to VTC sessions.

In order to provide the in-person or VTC SMART training, instructors must complete the Transform course in Rochester, MN or at another designated location. The Transform course consists of two days of initial classroom training, at least three months of distance-learning with [name], the developer of the SMART training, and a one-day, end-of-course classroom training.³² [name] (PI) has completed the Transform course, and [name] attended the two day classroom training July 17 and 18. She is in process of completing the distance-learning portion with [name].

In order to assure fidelity, [name] provides a standardized presentation, which is customizable by presenters. [name] has completed the Transform course and is approved to provide SMART training. During the initial delivery of the SMART training in month 3, [name] and [name] will make notations and jointly agree to incorporate recommendations for improving training delivery. At the end of the course, participants will be offered a copy of *SMART with [name]: The Four-Module Stress Management and Resilience Training Program* at no charge to the participants. This book will serve as a review of the practices and course content for improving gratitude, mindful presence, kindness, and developing a resilient mindset.

Additionally, in previous studies, individual participants were contacted by phone four weeks after attending the SMART course. These phone calls were offered to provide participants the opportunity to ask questions and to provide reinforcement of the principles presented during the SMART training.^{12, 15, 33-35} Therefore, study participants will be contacted by the PI two weeks after completing the SMART training by e-mail or phone and asked if they would like to schedule a follow-up phone meeting. If so, the PI will work to schedule a 30-minute follow-up phone call with participants. At the end of this follow-up session, participants will be provided the option to schedule a final 30-minute follow-up phone call. All phone consultations will be completed before the 12-week follow-up survey. These consultations will be a budget item for the proposed study and provided at no cost to participants.

Procedures. Letters of support have been received from the 88th MDG and USAFA Commanders. These letters of support includes permission to recruit potential participants with posted flyers, newspapers, social media, and informational e-mail announcements. Recruitment materials will be distributed in accordance with any limitations set by the governing IRBs and any future Commander instructions. Study information will be distributed as broadly as possible.

Initial recruitment and randomization will be completed during months 3 through 10 of the study. However, if the study team determines the need to recruit additional participants to ensure adequate statistical power, additional participants will be recruited in month 11 and 12. The study team will work with identified local points of contact to develop a schedule to assure the maximum number of participants can receive information about SMART during a variety of times. If approved by the chain of command, SMART could be completed during the participants' scheduled period of work. The study team will assure an IRB approved ombudsman will be present if informed consent is obtained in a group setting.

DISTRIBUTION C: Distribution authorized to U.S. Government agencies and their contractors (administrative).

Other requests for, or further releases of this document, shall be referred to

[name].

Improving Resiliency in U.S. Air Force Healthcare Personnel

AFRL IRB APPROVED 1 SEPTEMBER 2020

After informed consent is obtained and prior to the delivery of the intervention, a survey will be administered to collect demographic information and baseline measurements with the CD-RISC, PSS, GAD-7, and QoL measures. Participant demographic data, e-mail and phone contact information, and responses to survey items will be initially completed using a paper survey prior to the delivery of SMART and manually entered into the Research Electronic Data Capture System (REDCapTM; DHHS/NIH/NCRR #8UL1TR000041) by a study team member. If a participant prefers, they will be provided a web-link to enter the initial information directly into REDCapTM.

REDCapTM is a secure and encrypted, web-based platform licensed to and managed by the University of New Mexico Health Sciences Center Clinical and Translational Science Center (UNM HSC CTSC).³⁶ REDCapTM includes a suite of research tools for project management, survey administration, encrypted database storage and retrieval, and reporting.³⁶ REDCapTM will be utilized to administer follow-up surveys at week 12 and 24 (if applicable) after participants complete SMART. We propose to collect the 24-week follow-up survey responses in order to conduct an exploratory analysis to assess the longevity of the effect of SMART on resilience and stress.

Study team members will verify participant data has been entered correctly. Participant e-mail and phone contact information will be used to schedule a follow-up phone call two weeks after completing the SMART training (see intervention). Participants' e-mail contact information will be used to send follow-up surveys through REDCapTM. Each survey will take approximately 10 to 15 minutes for participants to complete. If the participant does not respond to the initial REDCapTM invitation, a maximum of three e-mail reminders (one reminder per week after the initial e-mail is sent) will be sent to complete the survey.³⁷ If a participant does not complete the survey after all e-mail requests have been sent, a study team member may call the participant to verify their e-mail information and offer to assist the participant with accessing the survey. Because participants' demographic information will be associated with an individual's contact information in REDCapTM, demographic information will not be requested as part of the surveys at weeks 12 or 24. All data will be de-identified prior to exporting the data for analysis.

Data Analysis. IBM[®] SPSS[®] Statistics (version 26) and R (survey package, version 3.61) will be used for the statistical analysis. Initial analysis will include descriptive statistics, including means or medians, frequencies and percentages, as appropriate, to characterize demographic status, military grade, duty location, military occupation, and previous deployment status. Cronbach's α will be calculated for each multi-item scale.

The objectives of our analysis include testing and estimating the efficacy of the intervention by comparing pre-post intervention changes (improvements) in the outcome measurements of interest. Analyses will be reported as point estimates with 95% confidence intervals and appropriate estimates of effect size. In this analysis, both the VTC and on-line groups will be analyzed separately and scores will also be pooled together to test for overall intervention effects.

To better understand factors that can impact the intervention effects, we will conduct regression models on the pre-post intervention difference while controlling for demographic characteristics,

DISTRIBUTION C: Distribution authorized to U.S. Government agencies and their contractors (administrative). Other requests for, or further releases of this document, shall be referred to
[name].

Improving Resiliency in U.S. Air Force Healthcare Personnel
AFRL IRB APPROVED 1 SEPTEMBER 2020

AFSC, and previous deployment. We will also take into consideration potential clustering effects among the participants from the same organizational unit using random effects (e.g. in regression models).

Changes in resilience, stress, anxiety, and QoL over time will be assessed by separately analyzing changes from baseline to week 12 and to week 24. A joint analysis of the longitudinal trend over the three time points at baseline, 12-week, and 24-week will be completed. We will also consider a joint analysis of resilience, stress, anxiety, or QOL, as well as, analysis for subscales of any specific domain of interest.

Section 7: Subject Selection

7.1 Do you plan to target a specific population for your study? Yes No

If Yes, please complete 7.2

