7.5.2 Consent Plan

Informed consent will be completed by a study team member after the completion of the described information sessions with individuals or groups. Any potential participant who wishes additional time to review the study information before providing consent will be able to do so. Participants will be provided with a copy of the consent document and will be informed that they may withdraw from the study at any time. Informed consent will be obtained from participants prior to baseline data collection.

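### Follow-up surveys are timed only from completing SMART, so a participant who does not finish has no visible 12-week survey date and the pre-post change describes those who completed training

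*Combined protocol and SAP*

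**What the plan says.** The survey trigger is stated twice in Section 6.1. Under Variables and Measures, surveys go out "at weeks 12 and 24 (if applicable) after participants complete SMART". Under Procedures, REDCap "will be utilized to administer follow-up surveys at week 12 and 24 (if applicable) after participants complete SMART". The opening design paragraph also counts the 12-week assessment from the training, and for the later one it says "A second post-test will be attempted for participants who completed the SMART training no later than the end of February 2021". Section 10.1 counts 12 weeks from the intervention.

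The two delivery types differ in what completing means. VTC is one scheduled two-hour session. Section 4 describes the alternative as a "self-paced, on-line version completed over a period of four to eight weeks". Section 6.1 (Intervention) adds: "Participants in the on-line training group will be provided a code to access the training website".

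Section 7.5.2 says participants "will be informed that they may withdraw from the study at any time". It does not say what happens to someone who stops the course but stays in the study.

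Section 6.1 (Data Analysis) analyses pre-post change in each delivery group and in both pooled. Sections 5.1 and 5.2 word the aim as effectiveness; Data Analysis and Section 10.1 use the word efficacy. The visible text gives no analysis set, no definition of completion and no missing-data method.

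**The concern.** If completion triggers the survey, adherence decides whose outcome is measured. A person who stops a self-paced course half-way may be quite willing to answer a 10 to 15 minute survey, but as written is not sent one. People who stop plausibly gain less than people who finish. If so, the reported change exceeds the change among all who were offered the training.

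The gap applies to both delivery types, since a VTC no-show has not completed SMART either. Partial completion is easier to foresee in a course lasting four to eight weeks than in one two-hour session.

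At stake are the size of the effect and the population it describes. A 12-week score that is not collected on time cannot be recovered, so the rule has to be settled before follow-up.

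**Working it through.** **Is there another route to a survey?**
- The three e-mail reminders and the telephone call in Section 6.1 follow an invitation already sent. They help with non-response, not with people never invited.
- The PI's two-week contact is also tied to completion: "study participants will be contacted by the PI two weeks after completing the SMART training by e-mail or phone".
- The right to withdraw concerns the study, not the course.
- The 25% attrition allowance in Section 10.1 protects power. It does not say who is missing.
- Attachment 1 (timeline) is listed but not shown, so it may or may not give a date.

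**The plan's own figures reproduce.** Inputs from Section 10.1 are two-sided alpha 0.05, 0.5 SD, up to 25% attrition, and a planned change of 7.7 (SD 8.7). Section 6.1 gives at least 60 per group.
- 60 × 0.75 = 45 per group.
- Paired t-test, n = 45, noncentrality 0.5 × √45 = 3.35: power 90.7%. For the Wilcoxon signed ranks test (effective n = 45 × 3/π) it is 89.3%. The plan says 90%.
- 7.7 / 8.7 = 0.885, inside the stated range of 0.8 to 0.9.

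None of these figures is disputed.

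**Illustration of size.** Assumptions not in the documents: s of 60 on-line participants do not finish, with s up to 15 (the whole attrition allowance); finishers gain 7.7; every finisher answers.

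Mean over all 60 = [(60 − s) × 7.7 + s × g] / 60, where g is the non-finishers' gain. Excess = 7.7 minus that mean, as a percentage of that mean.

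| s | mean, g = 0 | excess | mean, g = 3.85 | excess |
|---|---|---|---|---|
| 5 | 7.06 | 0.64 (9%) | 7.38 | 0.32 (4%) |
| 10 | 6.42 | 1.28 (20%) | 7.06 | 0.64 (9%) |
| 15 | 5.78 | 1.93 (33%) | 6.74 | 0.96 (14%) |

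Pooled over 120 with g = 0 and no VTC loss, the mean is (120 − s) × 7.7 / 120 = 7.38, 7.06 or 6.74, an excess of 4%, 9% or 14%.

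For scale, the 95% confidence half-width at n = 45 is 2.015 × 8.7 / √45 = 2.61 points.

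**Direction.** With s = 15, each non-finisher would have to fall by 45 × 7.7 / 15 = 23.1 points to cancel the on-line gain.

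**What surveying non-finishers buys (s = 15).** If r of the 15 answer and g = 0, the observed mean is 45 × 7.7 / (45 + r). For r = 5 it is 6.93, and the error falls from 1.93 to 1.16. For r = 10 it is 6.30, and the error falls to 0.53. This assumes that those who answer resemble those who do not. If the 5 who answer gained 3.85 and the 10 silent ones gained nothing, the all-60 mean is (346.5 + 19.25) / 60 = 6.10 and the observed mean is 365.75 / 50 = 7.32. The error then falls only from 1.60 to 1.22, or 24% less.

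**What it costs in power.** Take an effect of 0.5 SD in finishers, none in non-finishers, 45 finishers and r responding non-finishers. With f = 45 / (45 + r), the standardised mean is 0.5f / √[1 + 0.25f(1 − f)].
- r = 5: 0.445, power 87%
- r = 10: 0.402, power 83%
- r = 15: 0.367, power 80%

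At the planned 7.7 points, power stays above 99% in all three cases.

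**The case against.** The strongest reply is that change after receiving the training is what the plan means to estimate. Section 10.1 defines the primary outcome that way and labels it efficacy, and Data Analysis uses the same word. This stands: an estimate among recipients is a legitimate target, and replacing it would be a debatable change of estimand. It does not remove the gap, because the aim is worded as effectiveness and the plan cannot describe everyone offered the training if their scores are never collected.

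A reader might infer that the protocol prescribes a completers-only analysis. It does not. No such set is stated, completion is undefined, and one sentence about using e-mail addresses to send surveys carries no completion condition. The restriction follows only from applying the stated trigger.

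A reader might also infer that the on-line course will be made to look as good as VTC. Nothing visible says that on-line completion will be lower. Participants may switch to the type they prefer, which favours completion and makes any comparison by delivery type non-randomised. The plan specifies separate and pooled changes, not a formal comparison.

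Finally, the upper figures need all attrition to be non-finishing, no gain in non-finishers and full response from finishers. That is correct, and they should be read as an illustration.

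**Conclusion.** The point holds as a gap in data collection. Every visible follow-up date counts from completing or receiving SMART, and nothing visible invites a non-finisher. Unless the timeline attachment does so, the on-line, VTC and pooled changes will each describe people who completed training.

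The size is unknown. Under the assumptions above, the on-line figure is 9% to 33% above the all-participant mean if non-finishers gain nothing, and 4% to 14% above it if they gain half as much. At the half-gain level the error is 0.3 to 1.0 points, well inside the half-width of 2.6 at n = 45.

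The documents do not support the stronger conclusions that the finding of benefit is at risk, that the sample size is wrong, or that the main analysis must be replaced. The change is worth making because it is cheap now and impossible afterwards.

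**What to change.** 1. **Survey rule (Section 6.1, Variables and Measures and Procedures).** Send the 12-week survey to every participant given a session date or on-line code who has not withdrawn from the study. Finishers keep the current timing. For anyone who missed the session, week 0 is the session date. For anyone not recorded as complete 8 weeks after code issue, week 0 is that 8-week date, so the survey falls 8 + 12 = 20 weeks after code issue. That week 0 is kept for survey timing even if the person finishes later.
2. **Analysis (Section 6.1, Data Analysis).** Keep the analysis of participants who received the training, as planned in Section 10.1. Add the pre-post change in everyone given a date or code who returns a survey. Report the number not completing by delivery type.

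The two-week contact reinforces the training, so it can stay tied to completion.

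**Cost.** An IRB amendment, one REDCap scheduling rule, a recorded code-issue date, and a few extra e-mailed surveys (at most about 15 on-line within the attrition allowance) to addresses already held. If the timeline attachment already schedules non-finishers, only item 2 is needed.

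**Downsides.** Non-finishers will probably answer less often, so bias is reduced rather than removed. Their survey falls at a set date rather than 12 weeks after actual exposure; someone finishing in week 10 would be surveyed 10 weeks later. If non-finishers gain nothing, the added estimate has about 80% to 87% power at 0.5 SD with 15 down to 5 of them responding, against 90.7% for 45 finishers alone.
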